These occurrences will be logged in the practice where possible and identified from the NCSPR on completion of the study.

If a patient undergoes an off-study cytology test they will receive no further invitations for screening as part of the study.

Cytology triage (risk stratification)

As the incidence of hrHPV is higher than the incidence of CIN2 + and the risk of CIN2 or greater varies by the hrHPV type and cervical cytology findings, in most hrHPV screening programs, cytology is used to triage patients prior to colposcopy referral.

Reflex cytology process

If the sample has been performed as a clinician-based cervical sample, a liquid-based cytology examination will be performed in the reporting laboratory in the routine manner on the same specimen without further request. Reporting will be as per modified Bethesda (NZ) as per NCSP

recommendations. The pathologist's recommendation will be made as per NCSP guidelines, but it will also be noted that the patient is participating in the pilot study and study recommendations may vary from this. The report will be forwarded to the NCSP.

If a self-test hrHPV has been performed and hrHPV is detected, the patient will be recommended to undergo a clinician-taken cervical sample at their practice. This sample can be taken by any cervical screener. The cervical cytology will be performed in a routine manner at an accredited laboratory. The sample will be marked that the patient is taking part in the pilot study and the result of the hrHPV test. Reporting will be as above.

A patient with HPV16/18 will be referred directly to colposcopy. Because cytology is considered helpful to the colposcopist and to exclude other pathology a cervical cytology test is recommended for these participants, however it is not required and should not create a barrier for the participant. Patients who are experiencing symptoms should undergo a speculum examination cervical cytology and investigations as indicated.

Patients may choose to have the reflex cytology done at a non-participating practice. This is discouraged as it will make correlation of results more difficult. The cytology will then be performed and reported as per NCSP guidelines. The reporting pathologist may not be aware of prior hrHPV results and recommendation for referral will be made on the basis of cytology.

Patients with prior cervical abnormalities (Test of Cure)

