Data to be presented separately for participants negative for hrHPV, participants positive for HPV16 and/or 18, and participants positive for hrHPV other than 16 or 18.

The reason for no cytology report (prior to colposcopy) in participants positive for hrHPV and had a vaginal hrHPV test:

- Cytology not considered feasible by the GP
- Participant declined
- Participant unable to be contacted
- Other.

Data to be presented separately for participants positive for HPV16 and/or 18 and participants positive for hrHPV other than 16 or 18.

In participants that had a cytology test prior to colposcopy, the mean, median and range for the time between an hrHPV test result report being issued and a cytology sample being undertaken (prior to colposcopy).

Data to be presented separately for participants negative for hrHPV, participants positive for HPV16 and/or 18, and participants positive for hrHPV other than 16 or 18.

In participants that had a cytology test prior to colposcopy, the mean, median and range for the time from a cytology sample being undertaken to the results report being issued.

Data to be presented separately for participants negative for hrHPV, participants positive for HPV16 and/or 18, and participants positive for hrHPV other than 16 or 18.

In participants that had a cytology test prior to colposcopy, the number (and percentage) with a result of:

- Negative for dysplasia or malignancy
- ASC-US (atypical squamous cells of undetermined significance - excluding ASC-US possible high grade)
- LSIL (low grade squamous intraepithelial lesion)
- ASC-H (atypical cells of undetermined significance, possible high grade)
- HSIL (high grade squamous intraepithelial lesion)
- Cancer (invasive squamous carcinoma of the cervix)
- Adenocarcinoma
- Cancer other
- AGC/AIS (atypical glandular cells / adenocarcinoma-in-situ)
- Unsatisfactory sample

Data to be presented separately for participants negative for hrHPV, participants positive for HPV16 and/or 18, and participants positive for hrHPV other than 16 or 18.

In participants that had a cytology test prior to colposcopy, the mean, median and range for the time from their cytology sample being undertaken to being informed of the result.

Data to be presented separately for participants negative for hrHPV, participants positive for HPV16 and/or 18, and participants positive for hrHPV other than 16 or 18.

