In participants that had a cytology test prior to colposcopy, the number (and percentage) informed of their cytology results by:

- Face to face appointment with a staff member at their GP clinic
- Phone call with a staff member from their GP clinic
- Text
- Other form of contact.

Data to be presented separately for participants negative for hrHPV, participants positive for HPV16 and/or 18, and participants positive for hrHPV other than 16 or 18.

COLPOSCOPY

The mean, median and range for the time between an hrHPV test report being issued and GP referral for colposcopy.

Data to be presented separately by whether participants had a cervical or vaginal hrHPV test.

Data to also be presented separately for participants negative for hrHPV, participants positive for HPV16 and/or 18, and participants positive for hrHPV other than 16 or 18.

HPV-based Screening Implementation Study Protocol

In participants that had a cytology test prior to their colposcopy referral, the mean, median and range for the time between the cytology result report being issued and referral for colposcopy.

Data to be presented separately for participants negative for hrHPV, participants positive for HPV16 and/or 18, and participants positive for hrHPV other than 16 or 18.

The number (and percentage) of participants that had a referral for colposcopy by classification of urgency.

Data to be presented separately for participants negative for hrHPV, participants positive for HPV16 and/or 18, and participants positive for hrHPV other than 16 or 18.

In participants referred for colposcopy, the number (and percentage) that received 1, 2, 3 or >3 invitations for an appointment.

Data to be presented separately for participants negative for hrHPV, participants positive for HPV16 and/or 18, and participants positive for hrHPV other than 16 or 18.

In participants that had a colposcopy, the mean, median and range for time from GP referral to their colposcopy appointment.

Data to be presented separately for each classification of urgency.

Data to also be presented separately for participants negative for hrHPV, participants positive for HPV16 and/or 18, and participants positive for hrHPV other than 16 or 18.

In participants that had a cytology test during colposcopy, the number (and percentage) with a result of:

- Negative for dysplasia or malignancy
- ASC-US (atypical squamous cells of undetermined significance - excluding ASC-US possible high grade)

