In order to align with current NCSP practices, in terms of database requirements and automatic recall procedures, all patients in the clinician-taken sample group will have a cytology assessment of the sample they have already given, thus, do not need to return for a follow up cervical screen. The two groups, therefore, cannot be directly compared in terms of failure to return for follow up. In addition, as the clinician-taken and self-sample groups are self-selected they will be different and, hence, outcomes from the two groups will be recorded but cannot be directly compared.

Due to the relatively small size of this study and the unlikely outcome of a high-grade cervical abnormality, outcomes related to colposcopy referral will lack the power for stratification. However, the choice of screening method may usefully be able to be stratified.

Transfer of data and patient care to the NCSP.

The NCSPR will be informed of all patients participating in the study.

As the NCSPR is not currently able to manage the results of hrHPV screening this information will be overseen by the study team. The study team will act in place of the NCSPR to provide reminders to the practices when patients are overdue further investigations or repeat testing and to ensure management recommendations are correct. Following colposcopy or on completion of the study when the NCSPR is able to manage these patients' information they will be referred back to the NCSPR

Results of all cytology tests and hrHPV tests and colposcopy records will automatically be referred to the NCSPR. The study team will follow all patients to the end of the study to ensure patients who require colposcopy have been seen.

At completion of the study enrolled patients will fall under the following categories.

- Normal screen, next routine screen to be performed at the normal screening interval (5 years)
- Normal screen but because of previous abnormality follow up recommended in 12 months
- Abnormal screen referred to colposcopy attended follow up dictated by colposcopist and referred back to NCSP

- Abnormal screen colposcopy recommended lost to follow up/colposcopy declined
- Abnormal screen follow-up cytology advised but declined/lost to follow up
- Abnormal screen cytology performed follow up in 12 months recommended

This information will be shared with the NCSP (as far as possible in a manner that is suitable to the NCSP) and patients will be discharged to GP practice and NCSP

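### Time from hrHPV report to cytology sample pools self-testers' return visits with same-specimen cytology, so the row understates return delay and depends on test mix

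*Protocol*

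**What the plan says.** One row of the CYTOLOGY table under Outcome measures (Protocol) summarises "the time between an hrHPV test result report being issued and a cytology sample being undertaken (prior to colposcopy". Its opening words set the population: "In participants that had a cytology test prior to colposcopy, the mean, median and range for the time between an hrHPV test result report" and the taking of the cytology sample. The row sets one split: "Data to be presented separately for participants negative for hrHPV, participants positive for HPV16 and/or 18", with a third group positive for other hrHPV types. The general breakdowns listed under OTHER (screening history, age, ethnicity, deprivation, region) do not include test type.

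Where the cytology comes from depends on the test. For a clinician-taken test, Reflex cytology process says that "a liquid-based cytology examination will be performed in the reporting laboratory in the routine manner on the same specimen without further request". A positive self-tester is instead recommended to have a new clinician-taken sample. Statistical Considerations draws the consequence: the clinician-taken group need not return, and "The two groups, therefore, cannot be directly compared in terms of failure to return for follow up".

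Two nearby outcomes allow for this. The reason for having no cytology report is asked for only "in participants positive for hrHPV and had a vaginal hrHPV test". The report-to-referral time in the COLPOSCOPY table carries the instruction "Data to be presented separately by whether participants had a cervical or vaginal hrHPV test".

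**The concern.** The row has one clock but two kinds of participant. A self-tester's interval is the wait between a positive report and a return visit. After a clinician-taken test, the cytology sample was collected before the hrHPV report existed, so the interval is minus the sample-to-report time, or zero if the dates are coded that way. Averaging the two describes neither, and a split by hrHPV result does not separate them.

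Time to completion of the screening pathway is a primary objective, and the Equity section singles out the added cytology step as a possible new barrier. The pooled row pulls down the delay at that step. It also depends on how many people in a group chose each test. Since test choice is self-selected, two ethnic, deprivation or regional groups with identical return times could show different figures.

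**Working it through.** **The plan's own figures (Statistical Considerations).** Of 3000 participants, 60-70% are expected to self-test:
- 3000 × 0.60 = 1800 and 3000 × 0.70 = 2100, which leaves 1200 and 900 clinician-taken.
- At 12% positivity in self-tests, 1800 × 0.12 = 216 and 2100 × 0.12 = 252. These match the stated 216-252.

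**Share of same-specimen intervals among hrHPV positives.** Let s be the self-test share, p_self and p_clin the positivity rates, and r the share of positive self-testers who give a cytology sample. Then

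c = (1−s)·p_clin / [(1−s)·p_clin + s·p_self·r].

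The Protocol gives s and p_self = 12%. It gives no separate p_clin and no r. Appendix 4 gives about 7% (5-10%) for primary hrHPV screening overall; applying it to clinician-taken tests is an assumption.

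| Assumption | s = 0.70 | s = 0.60 |
|---|---|---|
| Equal positivity, r = 1 | 30% | 40% |
| Equal positivity, r = 0.8 | 0.30/(0.30+0.56) = 35% | 0.40/(0.40+0.48) = 45% |
| p_clin = 7%, r = 1 | 0.021/(0.021+0.084) = 20% | 0.028/(0.028+0.072) = 28% |
| p_clin = 5%, r = 1 | 0.015/(0.015+0.084) = 15% | 0.020/(0.020+0.072) = 22% |
| Equal positivity, r = 0.5 | 0.30/(0.30+0.35) = 46% | 0.40/(0.40+0.30) = 57% |

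The last line is meant for HPV16/18, where the Protocol recommends cytology after a self-test but does not require it; the 50% uptake is assumed. The range of about 15-57% is not a bound: 25% uptake would give 63-73%.

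**hrHPV-negative stratum.** Routine self-testers with a negative result are not recalled for cytology. Cytology here comes mainly from cervical samples taken for test of cure or symptoms, so most intervals would be same-specimen.

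**Effect on the mean.** With L the self-testers' true mean delay and T the sample-to-report time, the pooled mean is (1−c)·L − c·T. Assume L = 28 days and T = 7 days. (Handling of specimens recommends sending samples within 48 hours and sets reporting within 5 working days of receipt.)
- c = 15%: 0.85×28 − 0.15×7 = 22.8
- c = 30%: 0.70×28 − 0.30×7 = 17.5
- c = 40%: 0.60×28 − 0.40×7 = 14.0
- c = 57%: 0.43×28 − 0.57×7 = 8.1

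At c = 30% and 40%, L = 14 gives 7.7 and 5.6 days, and L = 60 gives 39.9 and 33.2 days. If same-specimen intervals are coded as zero, L = 28 gives 19.6 and 16.8 days, so the understatement is smaller but remains.

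**Effect on the median.** For c below 50%, the pooled median is the self-testers' percentile (0.5−c)/(1−c): 0.35/0.85 = 41st at 15%, 0.20/0.70 = 29th at 30%, 0.10/0.60 = 17th at 40%. Above 50% the median is itself a same-specimen value, zero or negative.

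**Effect of test mix.** Two groups with the same 28-day true mean, one with c = 30% and one with c = 40%, would report 17.5 and 14.0 days. That 3.5-day gap comes from test choice alone.

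**The case against.** The best defence is that the row was meant more narrowly. Earlier in the same table, cytology from the original cervical sample is separated from cytology done after the hrHPV test, and the row follows others on cytology invitations and on missing cytology after a vaginal test. Read in that order, it could mean the return visit only. But the row does not repeat the restriction, and its population phrase also governs the row of cytology results, where reflex samples must belong. The same phrase cannot mean later samples only in one row and all samples in the other.

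A second defence is that the dating of same-specimen cytology belongs in a statistical analysis plan, and that Statistical Considerations already treats the two groups as not comparable. Dating conventions can indeed wait. The population and the split, however, are set here, and recognising that the groups differ is a reason not to pool them.

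The defence is right on three stronger readings that a reader might infer:
- **That 30-40% of intervals are negative is not established.** It is the expected share choosing a clinician-taken test, and becomes a share of intervals only with equal positivity and full return.
- **The next two timing rows, sample to report and sample to being informed, do not have the same fault.** Both are valid positive intervals in both groups. For reflex cytology they include hrHPV processing, which is a real part of the wait.
- **The study does not lose its measure of failure to return.** Statistical Considerations restricts the three-month non-return count to self-testers, and Appendix 2 reports participants with other hrHPV who miss recommended cytology within three months.

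Subgroup breakdowns are also planned only where numbers permit, and no test or decision rule hangs on this row.

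**Conclusion.** The point holds for this one row. Followed as written, it mixes a real return delay with intervals that are zero or negative by construction. It therefore understates self-testers' delay and varies with test mix. The direction rests on the text alone, since a same-specimen sample cannot postdate its own hrHPV report. The size is not documented. The share of such intervals among hrHPV positives is 30-40% under equal positivity and full return, and about 15-57% under the other assumptions shown; the hrHPV-negative row would be mostly same-specimen. The effect in days rests further on assumed return and reporting times. The row is descriptive, but it serves a primary objective and is worth correcting.

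**What to change.** Restrict the row to participants with a vaginal hrHPV test and a separate, later cytology sample, and state that same-specimen cytology is excluded from the interval. At the least, present the row by cervical versus vaginal test, as the report-to-referral row already does, still excluding same-specimen cytology. Splitting the sample-to-report and sample-to-informed rows by test type is optional: it would help interpretation, but those rows are not wrong as they stand.

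The change is to the wording of one row. Test type is already an outcome, and the design is untouched. The price is smaller cells: on the plan's own estimate, at most 216-252 positive self-testers could contribute, fewer once divided by hrHPV type and subgroup.

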As a self-test is often more acceptable to patients than a clinician-taken cervical test, self-testing has been shown as an effective tool to improve participation in the screening program in un- or under-screened women⁷ and particularly in under-screened Māori women.⁸ The hrHPV self-test therefore has the potential to reduce the incidence of cervical cancer and reduce inequities in this disease for NZ patients.

It has previously been identified that a source of screening failure is delayed or inadequate response to an abnormal cervical screening test (*manuscript in preparation*). Delayed access to specialist assessment has also been identified as a source of inequity in NZ (*manuscript in preparation*). It is expected that hrHPV screening will identify more patients with cervical abnormalities than cytology screening so this will increase the imperative that assessment of patients following an abnormal test is effective and equitable.

It is also important to acknowledge that even with cytology triage, the introduction of primary hrHPV testing will increase demand on colposcopy services and that an overloaded colposcopy service will further reduce access to specialist assessment. An important focus of this study therefore is to document patient's access to cytology triage and colposcopy and the potential impact on colposcopy services.

The implementation of primary hrHPV screening incorporating self-testing is an important cancer control initiative. In order to implement this strategy, studies are needed to explore the uptake, efficiency, and equity of the strategy in a range of NZ populations. This study is designed to supply the NCSP and the NZ public with information that will assist the nationwide implementation of hrHPV testing.

Goal

The purpose of this study is to describe the impacts of implementing primary hrHPV-based cervical cancer screening incorporating the choice of vaginal self-testing or a clinician-taken cervical test in a diverse range of NZ primary care settings.

The impacts will be assessed by observing the events in the screening pathway from invitation to diagnosis of a precancerous change and identifying at which points, and for whom, the screening pathway fails.

Aims

To enrol a minimum of 15 primary care providers in differing environments throughout NZ to the study and offer the option of hrHPV screening to patients enrolled with their practice who are due for or overdue a cervical screen.

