To include the options of recall coordinated from within participating practices and centralised recall coordinated by the Primary Health Organisation (PHO).

To screen at least 3000 patients using their choice of one of the following tests:

- Vaginal hrHPV self-test performed at home or other suitable location
- Vaginal hrHPV self-test performed at the General Practice (GP) clinic (with or without nurse or kaiāwhina-led support)
- Clinician-taken cervical liquid-based cytology sample.

To implement NCSP-agreed care pathways for abnormal hrHPV screening results utilising cervical cytology, colposcopy and repeat screening.

To implement NCSP-agreed screening and care pathways for patients with previous abnormal cytology.

Objectives

Primary

To describe the impact of hrHPV testing (by demographics and screening history when numbers permit) in terms of:

- Proportion of patients screened by each method
- Proportion of patients who complete or do not complete each step of the appropriate screening pathway (including uptake of screening, cytology triage, and colposcopy assessment) and referral back to primary care
- Time to completion of the appropriate screening pathway
- Screening outcomes in patients with prior abnormalities in relation to transition guideline recommendations
- Number of colposcopy referrals, their indication, and outcomes.

To describe the disease burden detected in the study population, in terms of:

- HPV positivity rate by HPV 16/18 or other hrHPV, by demographics
- Incidence of CIN2+ in patients with HPV 16/18 by cytology result
- Incidence of CIN2+ in patients and with other hrHPV with abnormal cytology.

Secondary

To describe uptake of screening by mode of invitation:

- Centralised PHO or practice-based recall.

To describe resource utilisation (e.g. number of contacts, type of contact, engagement of other agencies, cost to patient) to achieve completion of the screening pathway:

- To achieve hrHPV screen
- In the event of an abnormal hrHPV screen, to achieve cervical cytology and/or colposcopy.

To report the rate of unsatisfactory hrHPV samples or documentation.

Equity

Compared to the general population, Māori and Pacific patients are less well served by the NCSP based in traditional primary care practices. The reason for introducing the HPV self-test is to reduce the incidence of cervical cancer and reduce inequities by providing a more sensitive test and reducing barriers to cervical screening.

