In participants who underwent hrHPV testing and had an unsatisfactory result, the number (and percentage) that: 
- Did have a repeat hrHPV test- Did not have a repeat hrHPV test.
In participants who underwent hrHPV testing and had a repeat test, the mean, median and range for time from the first hrHPV test and the repeat hrHPV test.

hrHPV RESULTS
The number (and percentage) of participants who had the following hrHPV result: 
- HPV 16- HPV 18- Other hrHPV (listed by genotype where available)- hrHPV not detected.

CYTOLOGY
The reason cytology was performed in participants that had cytology results issued from the sample taken during a cervical hrHPV test: 
- Requested by GP due to previous high grade lesion (test of cure)- Requested by GP due to previous abnormal cytology- Requested by GP due to symptoms- Requested by GP for other reason- Performed by laboratory due to detection of hrHPV (not GP requested)- Performed by laboratory due to identification of need to test for cure (not GP requested),- Other reason.
The reason cytology was performed in participants that had cytology performed after an hrHPV test and before colposcopy: 
- Positive for hrHPV result- Other reason. Data to be presented separately for participants negative for hrHPV, participants positive for HPV16 and/or 18, and participants positive for hrHPV other than 16 or 18.
The mean, median and range for the time from an hrHPV test result report being issued and the participant being informed of the result. Data to be presented separately for participants negative for hrHPV, participants positive for HPV16 and/or 18, and participants positive for hrHPV other than 16 or 18.

The number (and percentage) of participants informed of their hrHPV result by:

- Face to face appointment with a staff member at their GP clinic
- Phonecall with a staff member from their GP clinic
- Text
- Other form of contact.

Data to be presented separately for participants negative for hrHPV, participants positive for HPV16 and/or 18, and participants positive for hrHPV other than 16 or 18.

The number (and percentage) of participants with 0*, 1, 2 or 3 invitations for a cytology appointment, in participants who are recommended to have cytology.

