Appendix 1 *Data Management Plan (see separate document)*

Appendix 2 Safety and quality assurance plan

Introduction

This study is performed to determine the impact of implementation of hrHPV testing into the NCSP. The aim of screening is to prevent cervical cancer by the identification and treatment of the precursors to cervical cancer. While the NCSP has been a highly successful public health intervention, screening has its limitations and for individual screening failure can occur, this may be due to the inherent weaknesses of the test, diagnostic and treatment pathways, or failure of the process to be carried out correctly. It is well documented that the major cause of screening failure is non-engagement with the screening program, however, failure of the screening test to detect an abnormality and failure of the diagnostic and treatment pathway are also associated with a significant number of cancer occurrences. In addition, there are a number of service delivery interactions that may significantly affect the quality of a patient's experience which may in turn have an impact on future participation. It is well documented that the impact of these failures is inequitable.

The introduction of hrHPV testing will be associated with an increased sensitivity of the screening test and offers greater accessibility of the test and hence will improve the safety of the program. However, the change in procedures may increase, at least temporarily, the possibility of procedural or administrative errors. It is therefore important to monitor patient safety aspects of this study. This will be done by reporting adverse events, site visits, and auditing of data against source documents.

Identified risks

Major risks

Failure to detect significant abnormality (false negative test)

Patient given wrong result

Patient given inappropriate advice

Patient not informed regarding a positive result

Colposcopy for high grade cytology or HPV 16/18 not attended within 3 months

Inequity associated with participation

Other risks

Eligible patients not invited

Minimum invitation requirements not met

Patient positive for other hrHPV (i.e., non-HPV16/18) does not attend for cytology

Patient with other hrHPV (i.e., non-HPV16/18) does not attend for colposcopy

Serious adverse event reporting

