Serious adverse events will be reported to the study management team by filling out a Serious Adverse Event (SAE) report form and emailed within 7 days of the GP practice becoming aware of the event.

Serious Adverse Events include:

- Interval diagnosis of invasive cancer, CIN3, or AIS following a negative hrHPV test
- A screened person being given the wrong result
- A screened person being given the wrong advice following their screen (e.g., not referred to colposcopy or cytology when they should have been)
- A screened person not receiving the result of a positive test

Serious adverse events will be investigated as soon as possible by the study team and the relevant service provider to ensure similar errors do not occur and that there is no systemic case for this error.

The service provider will be responsible for the discussion of this adverse event with the person affected and their whanau and informing other agencies if appropriate. The study team will be responsible for informing the NCSP.

The following other adverse events will also be reported at completion of the study

- A person referred to colposcopy who does not attend within 3 months
- A person with other hrHPV who is recommended to have cervical cytology but who does not attend within 3 months

Site visits

Site visits will be performed either face to face or virtually by at least 1 member of the study management team, prior to commencing invitation to the study and within 3 months of commencing the study. Additional visits will be organised on request of the participating practice or if issues are perceived by the study management team.

The first visit is to ensure mechanisms of enrolment data management and clinical management of patients is understood by all members of the team. In addition, to ensure that systems are appropriate.

The second visit is to understand any issues of concern being encountered by the practice and to ensure ongoing participation of the practice team with screening and study protocols.

Further site visits may occur as required if areas of concern have been identified.

Audit

Prospectively-collected data will be collected in electronic case report forms (e-CRF) within 4 weeks of the event. 10% of data will be audited against source documents. If more than 10% of data is missing or incorrect, further in-depth audit will be undertaken.

Quality assurance

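### Colposcopy outcomes cannot separate a referral never booked or still waiting from a patient who did not attend

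*Protocol*

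**What the plan says.** **Colposcopy (Outcome measures).** Invitations are tabulated as "In participants referred for colposcopy, the number (and percentage) that received 1, 2, 3 or >3 invitations for an appointment". Waiting time is reported as "In participants that had a colposcopy, the mean, median and range for time from GP referral to their colposcopy appointment", so it covers only people who were seen. No item in the block asks why a referred person was not seen.

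**Cytology (Outcome measures).** The parallel items are "The number (and percentage) of participants with 0*, 1, 2 or 3 invitations for a cytology appointment, in participants who are recommended to have cytology" and "The reason for no cytology report (prior to colposcopy) in participants positive for hrHPV and had a vaginal hrHPV test". The second has four classes: not feasible, declined, not contactable, other.

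**Appendix 2.** Among the adverse events reported at completion of the study is "A person referred to colposcopy who does not attend within 3 months". The list of major risks uses similar wording: "Colposcopy for high grade cytology or HPV 16/18 not attended within 3 months".

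**Transfer of data and patient care to the NCSP.** Of the six end-of-study categories, the only one for a recommended colposcopy that did not take place joins loss to follow-up with refusal. None covers a referral not yet booked or a patient still waiting.

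**Objectives (Primary).** The study will describe the "Proportion of patients who complete or do not complete each step of the appropriate screening pathway", with colposcopy named as a step. The Background warns that "an overloaded colposcopy service will further reduce access to specialist assessment".

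**The concern.** The Goal is to locate where the pathway fails and for whom. At the colposcopy step it can fail in two ways: the service does not offer a timely appointment, or the patient is offered one and does not come. These need different remedies, and the Background treats access to colposcopy as an important focus. The section on the impact of Covid 19 says the results will indicate which groups did not engage with follow-up and where resources are needed. If the outputs describe an appointment never offered in patient-side terms, a capacity problem can be read as disengagement. The protocol provides for this distinction better at the cytology step, where it lists a zero class and reasons, than at the step where it expects service load to matter.

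**Working it through.** No stated figure is at issue. The check is to trace example referrals through the outputs as written, and then to set the scale.

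**Step 1: four example referrals**

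| Referral | Invitation class | Referral-to-appointment time | Completed? | Appendix 2 event | End-of-study category |
|---|---|---|---|---|---|
| A: never offered an appointment | none (in denominator only) | not included | no | yes | only lost/declined available |
| B: first offered after 3 months, attends | 1 | included, as a long wait | yes | yes | attended |
| C: offered three, declines all | 3 | not included | no | yes | lost/declined |
| D: sent one invitation, appointment still ahead at study end, more than 3 months after referral | 1 | not included | no | yes | only lost/declined available |

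A is marked only by the gap between the four classes and 100%. The protocol does not say that gap means zero invitations, and missing data would produce the same gap. D is identical in every column to a person invited once who did not come. B is separated by the waiting-time outcome but is still an event. A, C and D share the same event and the same closing category.

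**Step 2: scale**

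- Appendix 4 components per 1000 screened: 18 (HPV 16/18) + 8 (other hrHPV, high-grade) + 18 (other hrHPV, low-grade) = 44.
- Planned number screened: 3000. Expected referrals: 44 x 3 = 132.
- Appendix 4's percentages (7% positive, 25% of these HPV 16/18, 45% of the others with normal cytology) give 3000 x 0.07 x (0.25 + 0.75 x 0.55) = 139. The gap from 132 does not matter here. Over its 5-10% positivity range the same formula gives 99 to 199.
- Each misclassified referral moves the three-month event percentage by 100/132 = 0.76 points.

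**Step 3: why the size cannot be given**

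Let u be the share of referrals not offered an appointment within three months, and assume 10% of the rest do not attend. Neither rate is in the protocol. The event percentage is then u + 0.10(1 - u), and the service-side share of events is u / [u + 0.10(1 - u)].

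| u (assumed) | People, of 132 | Event percentage | Service-side share of events |
|---|---|---|---|
| 0% | 0 | 10% | 0% |
| 5% | 6.6 | 14.5% | 34% |
| 10% | 13.2 | 19% | 53% |
| 20% | 26.4 | 28% | 71% |

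The planned event count could not show which row applied. The table does not give the number with zero invitations: someone first invited after three months has an invitation class.

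**Step 4: the time windows**

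The Referral to colposcopy section asks that intermediate-risk (semi-urgent) patients be seen within 3 months, which is also the length of the Appendix 2 event window. Appendix 4 describes current low-grade referrals as seen within 26 weeks. A service booking to the latter figure would create events with no patient failing to attend. Appendix 4's other-hrHPV, low-grade group is 18 x 3 = 54 of the 132.

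**The case against.** The strongest reply is that most of the information survives. Everyone referred is in the denominator, and the number referred by urgency is itself an outcome, so an unbooked group shows as a shortfall. Completed and not-completed proportions are a primary objective. Late attenders appear in the waiting-time outcome. Appendix 2 is a safety list, and counting everyone not seen within three months, whatever the cause, suits that purpose. Reminders and study-team follow-up are planned, and Appendix 4 expects little effect on services. A reason code may exist in the separate Data Management Plan or the e-CRF.

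Much of this stands, and it rules out several stronger readings:

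- A reader might infer that unbooked referrals vanish. They do not, for the reasons just given.
- A reader might infer that every colposcopy outcome is conditional on having been seen. Time to referral and urgency class are defined on referral.
- A reader might infer that service delay and refusal receive the same value throughout. B and C coincide only in the Appendix 2 event.
- A reader might infer from Step 3 that non-attendance would be roughly doubled. That depends on two assumed, equal rates.
- A reader might infer that the events will be reported by ethnicity and region. The planned breakdown covers the listed outcomes when counts allow, and Statistical Considerations says colposcopy referral outcomes lack power for stratification.

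What the reply does not meet is the missing label. A shortfall carries no reason, reminders are not a reported outcome, and a field in another document is not used by any outcome stated here. The asterisk on the cytology zero has no visible note, so its exact meaning is unknown, but a zero class is plainly listed.

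**Conclusion.** The point holds in limited form. The invitation outcome has no zero class, no colposcopy outcome gives a reason for non-completion, and the only closing category and the three-month event are worded on the patient side. In these outputs a referral never booked or still waiting cannot be distinguished from patient non-attendance, although it remains in the denominator and in the completed/not-completed proportion. About 132 referrals are exposed, taking Appendix 4's 44 per 1000 and 3000 screened. How many would be affected is unknown, because the protocol gives no rate of unbooked or delayed referrals. It should be corrected because it bears on a primary objective and because the needed data must be collected prospectively. It does not invalidate the other colposcopy outcomes.

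**What to change.** 1. In the colposcopy invitation outcome, use classes 0, 1, 2, 3 and >3.
2. Add an outcome among all referred: number (%) with colposcopy completed and, for those without, the reason: no appointment offered or still waiting; declined; offered and did not attend; unable to be contacted; other.
3. In the end-of-study categories, add one for patients referred but not yet offered, or awaiting, an appointment.
4. Report the Appendix 2 three-month events split by whether an appointment had been offered within that time. State that this means an appointment falling inside the three months, so that referrals like D are placed correctly.
5. Reconcile the 3-month request in Referral to colposcopy, the 3-month event window in Appendix 2 and the current 26-week figure in Appendix 4 when these events are interpreted. Which interval is appropriate is not a matter for this review.

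The cost is one e-CRF reason field and one yes/no item on an appointment offered within three months. The reason field mirrors the cytology item. The yes/no item does not, and would have to come from the colposcopy services' records.
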